5.4.6.2 Adverse Events Occurring Secondary to Other Events

In general, adverse events occurring secondary to other events (e.g., cascade events or clinical sequelae) should be identified by their primary cause, with the exception of severe or serious secondary events. However, medically significant adverse events occurring secondary to an initiating event that are separated in time should be recorded as independent events on the Adverse Event eCRF. For example:

- If vomiting results in mild dehydration with no additional treatment in a healthy adult, only vomiting should be reported on the eCRF.
- If vomiting results in severe dehydration, both events should be reported separately on the eCRF.
- If a severe GI hemorrhage leads to renal failure, both events should be reported separately on the eCRF.
- If dizziness leads to a fall and subsequent fracture, all three events should be reported separately on the eCRF.
- If neutropenia is accompanied by an infection, both events should be reported separately on the eCRF.

All adverse events should be recorded separately on the Adverse Event eCRF if it is unclear as to whether the events are associated.

5.4.6.3 Persistent or Recurrent Adverse Events

A persistent adverse event is one that extends continuously, without resolution, between patient evaluation timepoints. Such events should only be recorded once on the Adverse Event eCRF. The initial severity (NCI CTCAE grade) of the event should be recorded at the time the event is first reported during Study GA28951. If a persistent adverse event becomes more severe, the most extreme NCI CTCAE grade should also be recorded on the Adverse Event eCRF. For adverse events reported as ongoing at the end of a parent study (i.e., the Phase II OLE study or a Phase III controlled study), the severity (NCI CTCAE grade) should be evaluated by the investigator at the start of Part 1 (OLE) and recorded in the "AE initial NCI CTCAE grade" field of the Adverse Event eCRF for Study GA28951. The most extreme NCI CTCAE grade for the event should also be recorded, taking into account the severity of the event since it was first reported during the parent study.

If the event becomes serious, it should be reported to the Sponsor immediately (i.e., no more than 24 hours after learning that the event became serious; see Section 5.5.2 reporting instructions). The Adverse Event eCRF should be updated by changing the event from "non-serious" to "serious," providing the date that the event became serious, and completing all data fields related to serious adverse events.

A recurrent adverse event is one that resolves between patient evaluation timepoints and subsequently recurs. Each recurrence of an adverse event should be recorded separately on the Adverse Event eCRF.

5.4.6.4 Abnormal Laboratory Values

Not every laboratory abnormality qualifies as an adverse event. A laboratory test result must be reported as an adverse event if it meets any of the following criteria:

- Accompanied by clinical symptoms
- Results in a change in study treatment (e.g., dosage modification, treatment interruption, or treatment discontinuation)
- Results in a medical intervention (e.g., potassium supplementation for hypokalemia) or a change in concomitant therapy
- Clinically significant in the investigator's judgment

It is the investigator's responsibility to review all laboratory findings. Medical and scientific judgment should be exercised in deciding whether an isolated laboratory abnormality should be classified as an adverse event.

If a clinically significant laboratory abnormality is a sign of a disease or syndrome (e.g., alkaline phosphatase and bilirubin 5× upper limit of normal [ULN] associated with cholecystitis), only the diagnosis (i.e., cholecystitis) should be recorded on the Adverse Event eCRF.

If a clinically significant laboratory abnormality is not a sign of a disease or syndrome, the abnormality itself should be recorded on the Adverse Event eCRF, along with a descriptor indicating if the test result is above or below the normal range (e.g., "elevated potassium," as opposed to "abnormal potassium"). If the laboratory abnormality can be characterized by a precise clinical term per standard definitions, the clinical term should be recorded as the adverse event. For example, an elevated serum potassium level of 7.0 mEq/L should be recorded as "hyperkalemia."

Observations of the same clinically significant laboratory abnormality from visit to visit should only be recorded once on the Adverse Event eCRF (see Section 5.4.6.3 for details on recording persistent adverse events).

5.4.6.5 Abnormal Vital Sign Values

Not every vital sign abnormality qualifies as an adverse event. A vital sign result must be reported as an adverse event if it meets any of the following criteria:

- Accompanied by clinical symptoms
- Results in a change in study treatment (e.g., dosage modification, treatment interruption, or treatment discontinuation)
- Results in a medical intervention or a change in concomitant therapy
- Clinically significant in the investigator's judgment

It is the investigator's responsibility to review all vital sign findings. Medical and scientific judgment should be exercised in deciding whether an isolated vital sign abnormality should be classified as an adverse event.

If a clinically significant vital sign abnormality is a sign of a disease or syndrome (e.g., high blood pressure), only the diagnosis (i.e., hypertension) should be recorded on the Adverse Event eCRF.

Observations of the same clinically significant vital sign abnormality from visit to visit should only be recorded once on the Adverse Event eCRF (see Section 5.4.6.3 for details on recording persistent adverse events).

5.4.6.6 Abnormal Liver Function Tests

The finding of an elevated ALT or AST ($>3 \times$ ULN) in combination with either an elevated total bilirubin ($>2 \times$ ULN) or clinical jaundice in the absence of cholestasis or other causes of hyperbilirubinemia is considered to be an indicator of severe liver injury (as defined by Hy's Law). Therefore, investigators must report as an adverse event the occurrence of either of the following:

- Treatment-emergent ALT or AST $>3 \times$ ULN, in combination with total bilirubin $>2 \times$ ULN
- Treatment-emergent ALT or AST $>3 \times$ ULN, in combination with clinical jaundice

The most appropriate diagnosis or (if a diagnosis cannot be established) the abnormal laboratory values should be recorded on the Adverse Event eCRF (see Section 5.4.6.4) and reported to the Sponsor immediately (i.e., no more than 24 hours after learning of the event), either as a serious adverse event or an adverse event of special interest (see Section 5.5.2).

5.4.6.7 Deaths

Part 1 OLE (Including the 12-Week Safety Follow-Up Period)

All deaths that occur during the protocol-specified adverse event reporting period (see Section 5.4.1), regardless of relationship to study drug, must be recorded on the Adverse Event eCRF and immediately reported to the Sponsor (see Section 5.5.2). This includes death attributed to progression of UC.

Death should be considered an outcome and not a distinct event. The event or condition that caused or contributed to the fatal outcome should be recorded as the single medical concept on the Adverse Event eCRF. Generally, only one such event should be reported. If the cause of death is unknown and cannot be ascertained at the time of reporting, “**unexplained death**” should be recorded on the Adverse Event eCRF. If the cause of death later becomes available (e.g., after autopsy), “unexplained death” should be replaced by the established cause of death. The term “**sudden death**” should not be used unless combined with the presumed cause of death (e.g., “sudden cardiac death”).

If the death is attributed to progression of ulcerative colitis, “ulcerative colitis progression” should be recorded on the Adverse Event eCRF.

Part 2 (SM)

If the investigator is made aware of an event of death, it should be reported directly to the Sponsor either by faxing or by scanning and emailing the Serious Adverse Event/Adverse Event of Special Interest Reporting Form with use of the fax number or email address provided to investigators (see “Protocol Administrative and Contact Information & List of Investigators”).

5.4.6.8 Preexisting Medical Conditions

Past resolved adverse events will be recorded in the medical history according to their medical relevance. Adverse events reported ongoing at the end of the Phase II OLE or Phase III studies will be stated unresolved in those studies and reopened in Study GA28951.

A preexisting medical condition should be recorded as an adverse event only if the frequency, severity, or character of the condition worsens during the study. When recording such events on the Adverse Event eCRF, it is important to convey the concept that the preexisting condition has changed by including applicable descriptors (e.g., “more frequent headaches”).

5.4.6.9 Lack of Efficacy or Worsening of Ulcerative Colitis

Medical occurrences or symptoms of deterioration that are anticipated as part of UC should be recorded as an adverse event if judged by the investigator to have unexpectedly worsened in severity or frequency or changed in nature at any time during the study. When recording an unanticipated worsening UC on the Adverse Event eCRF, it is important to convey the concept that the condition has changed by including applicable descriptors (e.g., “accelerated ulcerative colitis” or “worsening of ulcerative colitis”).

5.4.6.10 Hospitalization or Prolonged Hospitalization

Any adverse event that results in hospitalization (i.e., in-patient admission to a hospital) or prolonged hospitalization should be documented and reported as a serious adverse event (per the definition of serious adverse event in Section 5.3.2), except as outlined below. The duration of hospitalization should also be noted on the eCRF.

An event that leads to hospitalization under the following circumstances should not be reported as an adverse event or a serious adverse event:

- Hospitalization for respite care
- Planned hospitalization required by the protocol (e.g., for study drug administration or insertion of access device for study drug administration)
- Hospitalization for a preexisting condition, provided that all of the following criteria are met:

The hospitalization was planned prior to the study or was scheduled during the study when elective surgery became necessary because of the expected normal progression of the disease.

The patient has not suffered an adverse event.

An event that leads to hospitalization under the following circumstances is not considered to be a serious adverse event, but should be reported as an adverse event instead:

- Hospitalization that was necessary because of patient requirement for outpatient care outside of normal outpatient clinic operating hours

5.4.6.11 Adverse Event Associated with Overdose or Error in Drug Administration

Study drug overdose is the accidental or intentional use of the drug in an amount higher than the dose being studied. An overdose or error in administration of study drug is not itself an adverse event, unless it results in an adverse event.

Any study drug overdose or error in administration of study drug (e.g., dosing outside of the allowed window and injection without completion of full volume administration) should be noted on the Study Drug Administration eCRF.

All adverse events associated with an overdose or error in administration of study drug (e.g., dosing outside of the allowed window and injection without completion of full volume administration) should be recorded on the Adverse Event eCRF. If the associated adverse event fulfills serious criteria, the event should be reported to the Sponsor immediately (i.e., no more than 24 hours after learning of the event; see Section 5.5.2).

5.4.6.12 Patient-Reported Outcome Data

Adverse event reports will not be derived from patient-reported outcome (PRO) data by the Sponsor, and safety analyses will not be performed using PRO data. *Sites are not expected to review the PRO data for adverse events.*

5.5 IMMEDIATE REPORTING REQUIREMENTS FROM INVESTIGATOR TO SPONSOR DURING PART 1 AND PART 2

Certain events require immediate reporting to allow the Sponsor to take appropriate measures to address potential new risks in a clinical trial. The investigator must report such events to the Sponsor immediately; under no circumstances should reporting take place more than 24 hours after the investigator learns of the event. See Section 5.5.2 for reporting requirements in Part 1 (OLE) and Part 2 (SM).

The following is a list of events that the investigator must report to the Sponsor within 24 hours after learning of the event, regardless of relationship to study drug:

- Serious adverse events (see Section 5.5.2 for further details)
- Adverse events of special interest (see Section 5.5.2 for further details)
- Pregnancies (see Section 5.5.3 for further details)

The investigator must report new significant follow-up information for these events to the Sponsor immediately (i.e., no more than 24 hours after becoming aware of the information). New significant information includes the following:

- New signs or symptoms or a change in the diagnosis
- Significant new diagnostic test results
- Change in causality based on new information
- Change in the event's outcome, including recovery
- Additional narrative information on the clinical course of the event

Investigators must also comply with local requirements for reporting serious adverse events to the local health authority and IRB/EC.

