5.4.2 Adverse Event Reporting Period for Part 2 (SM)

Part 2 (SM) of the OLE-SM study is focused on extended follow-up for PML. During Part 2 (SM) the investigator will use the PML assessment interview to monitor for signs and symptoms of PML. The investigator is not required to actively monitor patients for other adverse events in Part 2 (SM); however, if he or she becomes aware of any other non-PML serious adverse events that are believed to be related to any prior study drug treatment, these should be reported to the Sponsor.

The investigator should report such events directly to Roche or its designee either by faxing or by scanning and emailing the Serious Adverse Event/Adverse Event of Special Interest Reporting form with use of the fax number or email address provided to investigators.

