5.5.2 Reporting Requirements for Serious Adverse Events and Adverse Events of Special Interest

Part 1 (OLE)

For reports of serious adverse events and adverse events of special interest, investigators should record all case details that can be gathered immediately (i.e., within 24 hours after learning of the event) on the Adverse Event eCRF and submit the report via the EDC system. A report will be generated and sent to Roche Safety Risk Management by the EDC system.

In the event that the EDC system is unavailable, the paper Clinical Trial Serious Adverse Event/Adverse Event of Special Interest Reporting Form provided to investigators should be completed and submitted to the Sponsor or its designee immediately (i.e., no more than 24 hours after learning of the event), either by faxing or by scanning and emailing the form with use of the fax numbers or email address provided to investigators. Once the EDC system is available, all information will need to be entered and submitted via the EDC system.

Part 2 (OLE)

Reports of non-PML serious adverse events, that the investigator becomes aware of and believes to be related to prior study drug treatment will be reported via a direct report to the Sponsor either by faxing or by scanning and emailing the Serious Adverse Event/Adverse Event of Special Interest Reporting Form with use of the fax number or email address provided to investigators (see "Protocol Administrative and Contact Information & List of Investigators").

Instructions for reporting post-study adverse events are provided in Section [5.7](#).

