5.5.3.4 Congenital Anomalies/Birth Defects

Any congenital anomaly/birth defect in a child born to a female patient exposed to study drug or the female partner of a male patient exposed to study drug should be classified as a serious adverse event, recorded on the Adverse Event eCRF, and reported to the Sponsor immediately (i.e., no more than 24 hours after learning of the event; see Section 5.5.2).

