6.4 SAFETY ANALYSES FOR PART 2 (SM)

In Part 2, any suspected or confirmed PML events will be listed and described by means of safety narratives.

Serious adverse events (including serious infections) and deaths will also be described as narratives.

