- ^a The total length of the PML monitoring period is 104 weeks after the patient discontinues from the study (12-week safety follow-up plus 92-week extended PML monitoring period). The extended PML monitoring period telephone calls will occur at the indicated timepoints for the 92-week extended PML monitoring period. The extended PML monitoring will be conducted using a PML Subjective Checklist over the telephone. PML monitoring should occur within 7 days of the specified day.
- ^b Unscheduled telephone call represents a call that is not as per Schedule of Assessments and it is symptom driven.
- ^c If the patient discontinues after the 12-week safety follow-up visit but prior to study completion (end of extended PML monitoring period), the early termination visit from the extended PML monitoring period should be performed (a subjective checklist by telephone).
- ^d Unscheduled visit represents a visit that is not as per Schedule of Assessments and it is symptom driven.
- ^e If there are any signs or symptoms suggestive of PML identified on the subjective checklist during the telephone call, the patient will be asked to come into the clinic for a neurologic examination, including administration of the PML Objective Checklist.
- ^f Investigators are not required to actively monitor patients for adverse events; however, if he or she becomes aware of any other serious adverse events that are believed to be related to prior study drug treatment, these should be reported directly to Roche or its designee either by faxing or by scanning and emailing the Serious Adverse Event/Adverse Event of Special Interest Reporting Form with use of the fax number or email address provided to the investigators. The investigator may become aware of such events at these timepoints or via other means, but the data are not to be collected routinely.

Appendix 4

Childbearing Potential, Pregnancy Testing, and Contraception

All women of childbearing potential (including those who have had a tubal ligation) will have a urine pregnancy test prior to administration of study drug at subsequent visits. If a urine pregnancy test result is positive, study drug will not be administered that day. The result must be confirmed by a serum pregnancy test (conducted by the central laboratory). Refer to Section 5.5.3 of the protocol for management of a patient with a confirmed pregnancy.

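### For non-fatal, non-PML serious adverse events in Part 2 the protocol states two incompatible reporting rules, and Section 6.4 does not say which events its narratives cover

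*Protocol*

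**What the plan says.** Two groups of sections in the current protocol govern SAEs in Part 2.

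**No causality condition.** Section 5.5 is headed "IMMEDIATE REPORTING REQUIREMENTS FROM INVESTIGATOR TO SPONSOR DURING PART 1 AND PART 2". It lists SAEs, adverse events of special interest and pregnancies as events the investigator "must report to the Sponsor within 24 hours after learning of the event, regardless of relationship to study drug". Section 5.3.2 also asks for all SAEs within 24 hours, without distinguishing the two parts.

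**Related events only.** Section 5.4.2, on the Part 2 reporting period, asks for "any other non-PML serious adverse events that are believed to be related to any prior study drug treatment" if the investigator becomes aware of them. The Part 2 paragraph of Section 5.5.2, which carries the label Part 2 (OLE) instead of Part 2 (SM), covers non-PML SAEs "that the investigator becomes aware of and believes to be related to prior study drug treatment". Appendix 3 footnote f asks for "any other serious adverse events that are believed to be related to prior study drug treatment". All three send the report by fax or email on the SAE/AESI form. Section 5.4.2 and footnote f add that active monitoring for other events is not required, and footnote f that such data are not gathered routinely.

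**Related provisions.** Section 5.4.6.7 takes any Part 2 death of which the investigator is made aware, with no causality condition. Section 5.5.3.3 treats any abortion as an SAE for the Adverse Event eCRF. Under Section 5.5.3.4 a congenital anomaly "should be classified as a serious adverse event, recorded on the Adverse Event eCRF, and reported to the Sponsor immediately".

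**Use of the data.** For Part 2, Section 6.4 plans listings and narratives of PML events and adds: "Serious adverse events (including serious infections) and deaths will also be described as narratives". It mentions no causality limit. The SAP covers the Part 1 objective only, so Section 6.4 is the only description of Part 2 safety reporting in the two documents.

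**The concern.** An investigator who learns during a Part 2 call of a non-fatal serious infection, and judges it unrelated, finds that Section 5.5 requires a report within 24 hours and that Section 5.5.2 does not require one. Two careful sites could act differently, and neither would clearly be in breach.

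Two things depend on the answer. The first is what the Section 6.4 narratives represent: all serious events that came to the notice of sites, only those attributed to study drug, or some of each. The second is what the sponsor can review. Section 5.8 allows the sponsor to upgrade the investigator's causality assessment, but it cannot upgrade an event it never receives.

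**Working it through.** The plan gives no figure to reproduce, so the check sets the rules side by side for each kind of event an investigator may learn of in Part 2.

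| Event in Part 2 | Sections 5.5 and 5.3.2 | Sections 5.4.2, 5.5.2, Appendix 3 footnote f | Other section |
|---|---|---|---|
| Non-fatal, non-PML SAE judged unrelated | Report, 24 hours | No report required | None |
| Non-fatal, non-PML SAE judged related | Report, 24 hours | Report by fax or email form; no Part 2 time limit given | None |
| Death | Report the fatal SAE, 24 hours | Report the SAE only if believed related | 5.4.6.7: report, no causality condition |
| Suspected or confirmed PML | Report, 24 hours | Outside the related-only limit | 5.2: report, 24 hours |
| Abortion or birth defect | Report as SAE, 24 hours | Report only if believed related, by fax or email form | 5.5.3.3 and 5.5.3.4: report any, 24 hours, on the eCRF |

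**Row 1** is a direct contradiction. Two sections ask for the event, one of them (5.5) expressly whatever the relationship, and three do not ask for it.

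**Row 2** agrees on whether to report but not on timing. The 24-hour limit comes only from 5.5 and 5.3.2, because the Part 2 paragraph of 5.5.2 states none. A site must therefore apply 5.5 in Part 2 for the deadline while setting aside its causality wording.

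**Row 3** is settled by the specific rule for deaths. The same illness judged unrelated is reportable if fatal, and is disputed between sections if not.

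**Row 4** is consistent. PML reporting is not affected.

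**Row 5** conflicts on causality and on route. It can arise in Part 2, because Section 5.5.3.1 asks patients to report pregnancies during the study or up to 24 weeks after the last dose:
- If the 12-week safety follow-up is counted from the last dose, the 24-week window runs 24 − 12 = 12 weeks into Part 2.
- If it is counted from an early withdrawal visit 30 days after the last dose (the limit in Appendix 1 footnote d), the overlap is 24 − 12 − 30/7 = 7.7 weeks.

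**Extent in time.** Appendix 3 footnote a gives 12 + 92 = 104 weeks of follow-up. The conflicting rules apply for 92/104 = 88.5% of it, in up to about 2100 patients. This describes where the conflict applies. It does not estimate how many events are affected.

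**The case against.** The best reply is that Section 5.5.2 is simply the specific rule. Section 5.5 sends the reader there for the requirements in each part, and its SAE bullet repeats the pointer. The section on the Part 2 reporting period and the Part 2 schedule, which a site is most likely to use, both say related-only. The same limit applies to patients who decline Part 2 (5.4.1, 5.7.1) and to post-study events (5.7.2). It also looks deliberate: PML is the only Part 2 outcome measure (3.3.3), Section 5.3 confines Part 2 safety assessment to PML monitoring, and the amendment summary shows that causality was considered for Part 2 deaths specifically.

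Most of this stands, and it makes related-only the likelier intention. It does not settle the matter. Section 5.5 does not restrict its wording to Part 1, and 5.5.2 does not present itself as an exception. The mislabelled paragraph and the missing deadline make 5.5.2 a poor self-contained rule.

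The practical effect is also limited. The causality guidance in Section 5.4.5 defaults to related, which narrows the filter. Collection is passive under either rule, so removing the causality condition would not give complete ascertainment. Section 6.4 plans narratives and no rates.

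**Conclusion.** The protocol contradicts itself on whether a non-fatal, non-PML SAE judged unrelated must be reported in Part 2. It is also inconsistent on the time limit and, for abortions and birth defects, on the route. The consequence is that sites following different sections could report different events, and the Section 6.4 narratives would then have no defined basis. That such a mixture will occur is not established; it depends on how sites read the sections. The conclusion rests on the text alone and needs no assumed rate. Part 1 analyses and the Part 2 PML outcome are unaffected.

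Three stronger readings are not supported:
- **A count of missed malignancies.** The documents give no malignancy rate. A count would also need every patient to enter and complete Part 2, every case to reach the investigator under passive collection, and none to be judged related or to be fatal. Malignancy incidence is a Part 1 outcome measure.
- **A flaw from blinded judgement.** Some patients enter Part 2 directly from double-blind studies, but judging relatedness without knowing the arm is ordinary in such studies, and the test in Section 5.4.2 refers to any earlier study drug.
- **A need for active collection of other events.** Part 2 was designed for PML, and the contradiction can be removed without widening that purpose.

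**What to change.** Reconcile Sections 5.3.2, 5.4.2, 5.5, 5.5.2 and 5.5.3 and Appendix 3 footnote f so that Part 2 has one causality rule, one time limit and one reporting route. Either of two choices does this:

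1. **Narrower rule.** Add to Section 5.5 that, in Part 2, the causality condition, time limit and route in Section 5.5.2 replace those given there, and put a time limit into 5.5.2.
2. **Broader rule.** Apply the wording of Section 5.5 to every SAE the investigator becomes aware of in Part 2, with causality recorded on the existing form. No active monitoring is added.

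A rule for selected event types only would match neither existing rule and would add a third.

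Under either choice, correct the Part 2 (OLE) label in 5.5.2 and state which form carries abortions and birth defects in Part 2. Section 6.4 should say that non-PML SAEs in Part 2 are passively collected, and whether the narratives cover all reported SAEs or only those judged related. Because Part 2 spans patients who stopped treatment at different times, Section 6.4 should also give the date from which any changed rule applied, so that events collected under different rules can be told apart.

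The cost is amendment wording. The broader rule adds some case processing for events that sites already learn of.
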